7.3.2.1 Data Handling of Worst Leg Pain

The mean worst leg pain score from 7 consecutive days prior to each visit will be targeted as the worst leg pain score for each time point; (the day of the visit itself will not be included but will serve as the anchor). If less than 3 days of worst leg pain scores are available in the day interval prior to a visit, alternative 7-day intervals within the protocol-specified visit window will be examined. Finally, for the Week 52 visit only, if the actual visit day falls outside of the protocol-defined window, intervals in that window will be targeted first. Note that post-baseline visits were scheduled per the protocol with the injection date as day 1; in rare instances, this may be after the randomization date. For the purposes of the below algorithm, the injection date is considered to be day 1.

To calculate the 7-day average, first the worst leg pain score on any of the following days will be eliminated:

- Days after prohibited concomitant therapies of lumbar operation, lumbar percutaneous nucleotomy, or lumbar intradiscal therapies occurred, and
- Days before the previous visit (for example, the Week 2 visit may fall just 5 days after Week 1; thus, the days prior to the Week 1 visit will not be considered as eligible for inclusion in the 7-day Week 2 average).

Anchored by the visit date, the average of the consecutive days prior to each visit will be calculated. If less than 3 days of worst leg pain scores are available of the 7 consecutive days prior to a visit, the following approach will be utilized:

1. Using the visit target day, each day that would fall within the protocol-defined visit window will be identified as the anchor.
2. For each of those days, the corresponding 7 day interval anchored to that end date will be examined and all intervals with a valid average with at least 3 days of data will be identified
3. The interval with the anchor day that falls closest to the visit target day will be selected for the average. In the case of two equidistant valid intervals, the one with the later anchor day will be used.

If an in-person visit is missing altogether, the above process will be used with the corresponding visit target day. If no valid interval can be identified, worst leg pain score will be handled as missing at the time point.

Finally, for the Week 52 visit, if the actual visit day falls outside of the protocol-defined window, the following approach will be utilized:

1. Each day from day 351 to day 379 will be identified as a possible anchor.
2. For each of those days, the corresponding 7 day interval anchored to that end date will be examined and all intervals with a valid average with at least 3 days of data will be identified
3. The interval with the anchor day that falls closest to day 365 will be selected for the average. In the case of two equidistant valid intervals, the one with the later anchor day will be used.

If no valid interval is identified anchoring from day 351 to day 379 (365 +/- 14 days), only then will the interval anchored by the out-of-window visit be used.

The data handling for the worst back pain will use rules identical to those above for worst leg pain.

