9.2.4 Visit 3: Week 1 (Day 8 ±1 day)

The following activities will be performed at Visit 3 (Week 1).

- Complete ODI assessment.
- Collect concomitant medication and therapy information.
 - Confirm use and amount of concomitant medication(s)/therapy(ies).
 - Assess use of restricted medication(s)/therapy(ies) for LDH.
- Review the subject daily diary and assess compliance.
- Collect vital signs.
- Record AEs.
- Perform neurological examination.
- Perform urine drug test for subjects prescribed hydrocodone/acetaminophen rescue.
- Collect blood sample for laboratory tests (hematology and chemistry panels).
- Provide instructions for recording daily pain assessment and rescue medication use.
- Distribute acetaminophen rescue, as described in Section 6.6.4.
- As applicable per Section 6.6.4, distribute hydrocodone/acetaminophen rescue medication. Discuss usage and counsel, as appropriate.
- Remind subject to avoid any strenuous activities.

9.2.5 Visits 4 and 5: Week 2 (Day 15 ±3 days) and Week 4 (Day 29 ±3 days)

The following activities will be performed at Visit 4 (Week 2) and Visit 5 (Week 4):

- Complete the ODI, SF-36, and PGIC assessments (SF-36 will not be performed at Visit 4).
- Collect concomitant medication and therapy information.

- Confirm use and amount of concomitant medication(s)/therapy(ies).
- Assess use of restricted medication(s)/therapy(ies) for LDH.
- Collect vital signs.
- Record AEs.
- Perform neurological examination.
- Perform urine drug test for subjects prescribed hydrocodone/acetaminophen rescue.
- Complete the CGIC assessment.
- Provide instructions for recording daily pain assessment and rescue medication use.
- Distribute acetaminophen rescue, as described in Section 6.6.4.
- As applicable per Section 6.6.4, distribute hydrocodone/acetaminophen rescue medication. Discuss usage and counsel, as appropriate.
- Remind subject to avoid any strenuous activities.

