9.5 Efficacy Assessments

9.5.1 Pain Intensity

- Assessment Points: Daily from screening until Week 52
- Item: Worst leg pain and worst low back pain during the past 24 hours assessed by 100 mm VAS
- Method: The 100 mm VAS pain assessment tool will be used to measure pain intensity. At the screening visit, the investigator will provide a daily diary and instruct subjects to record daily the pain intensity from LDH over the last 24 hours basically before going to bed.

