11.8 General Considerations

11.8.1 Data Handling of Worst Leg Pain

The mean worst leg pain score from 7 consecutive days prior to each visit (the day of the visit will not be included) will be used as the worst leg pain score for each time point, after excluding the worst leg pain score on any of the following days:

- Days after prohibited concomitant therapies of lumbar operation, lumbar percutaneous nucleotomy, or lumbar intradiscal therapies occurred, and
- Days before the previous visit (for example, the Week 2 visit may fall just 5 days after Week 1; thus, the days prior to the Week 1 visit will not be considered as eligible for inclusion in the 7-day Week 2 average).

In addition, if less than 3 days of worst leg pain scores are available of the 7 consecutive days prior to a visit, the worst leg pain score will be handled as missing at the time point.

For the separate analysis of the weekly pain scores throughout the study, an average of the scores every 7 days will be calculated regardless of the visit date.

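### For Week 1 visits on Day 7 or Day 8, the leg and back pain averages keep the injection-day diary score, whose 24-hour recall includes hours before the injection

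*SAP*

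**What the plan says.** SAP 7.3.2.1 builds each pain score from a week of diary entries: "The mean worst leg pain score from 7 consecutive days prior to each visit will be targeted", where "the day of the visit itself will not be included but will serve as the anchor". On day numbering it adds: "For the purposes of the below algorithm, the injection date is considered to be day 1". Protocol 9.2.4 places the Week 1 visit on Day 8 with a window of one day either side.

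Two kinds of day are removed before averaging. The first is "Days after prohibited concomitant therapies of lumbar operation, lumbar percutaneous nucleotomy, or lumbar intradiscal therapies occurred". The second, in the Protocol 11.8.1 wording that the SAP repeats, is "Days before the previous visit (for example, the Week 2 visit may fall just 5 days after Week 1", with the earlier days then dropped. An average needs at least three scores. SAP 7.3.2.1 extends the same rules to worst back pain; Protocol 11.8.1 is written for leg pain only.

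The diary item is the worst pain of the past 24 hours. Under Protocol 9.5.1 the investigator is to "instruct subjects to record daily the pain intensity from LDH over the last 24 hours basically before going to bed".

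**The concern.** Week 1 is presented as the first post-treatment time point. For an on-schedule visit, however, one of its daily scores is a maximum over a 24-hour period that straddles the injection. One bad hour beforehand can set that score, so some of what is reported as Week 1 pain may be pre-treatment pain.

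The content of the Week 1 average also changes with scheduling: a visit on Day 7 or Day 8 includes the injection day and a visit on Day 9 does not.

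At stake is the change from baseline in leg and back pain at Week 1. It is a listed secondary outcome (Protocol 8.1.3, SAP 7.2), is compared between arms at each time point (SAP 7.3.3.3), and for leg pain is the first repeated measure in the primary model.

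**Working it through.** The plan gives no figure for the share of the injection day in the Week 1 average, so there is none to reproduce. The check is a day count.

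**Inputs.** Injection = Day 1, visit day excluded, seven days before the visit, two exclusion rules, minimum of three scores (SAP 7.3.2.1). Week 1 visit on Day 7, 8 or 9 (Protocol 9.2.4). The day before Day 1 is Day -1; there is no Day 0 (Protocol 9.2.2).

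**Step 1: do the exclusions remove Day 1?** The first concerns days after a prohibited lumbar procedure and does not apply to the study injection. The second removes days before the previous visit. For Week 1 that is Visit 2, and Day 1 is the day of Visit 2 treatment, not a day before it. Day 1 stays.

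**Step 2: which days are averaged, and with what weight?** With k scores available, Day 1 has weight 1/k. The table takes Visit 2 as dated Day 1.

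| Week 1 visit | Days averaged | Day 1 weight, complete diary |
|---|---|---|
| Day 7 | 1–6 | 1/6 = 16.7% |
| Day 8 (target) | 1–7 | 1/7 = 14.3% |
| Day 9 | 2–8 | not included |

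With only three scores, one of them from Day 1, the weight is 1/3 = 33.3%. The SAP's fallback search for another interval contains no rule against Day 1 either.

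**Step 3: what could this do to the Week 1 difference?** Assume that Day 1 carries no treatment effect and every later day carries a constant difference d. The observed difference is then d × (1 − 1/k). The documents give no expected Week 1 difference, so a range is shown; 12 mm is the planning difference for the primary analysis (SAP 2.6).

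| d (mm) | k = 7 (× 6/7) | k = 6 (× 5/6) | k = 3 (× 2/3) |
|---|---|---|---|
| 3 | 2.6 | 2.5 | 2.0 |
| 6 | 5.1 | 5.0 | 4.0 |
| 12 | 10.3 | 10.0 | 8.0 |

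**Step 4: do later time points contain the injection day?** The earliest in-window Week 2 visit is Day 15 − 3 = Day 12, which uses no day before Day 5. The earliest Week 13 visit is Day 92 − 7 = Day 85, which uses Days 78–84. The earliest Week 52 visit is Day 365 − 14 = Day 351, which uses Days 344–350. None includes Day 1.

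**Step 5: after the change in the fix.** A Day 7 visit averages Days 2–6 (5 scores), a Day 8 visit Days 2–7 (6 scores), and a Day 9 visit Days 2–8 (7 scores, as now).

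**The case against.** **The direction is not established.** This is the strongest objection, and it stands. The Day 1 score is a maximum over the hours before the injection, the procedure and the hours after. Only the active arm has a needle in the disc and 1.0 mL injected (Protocol 6.4). Protocol 1.2.1.2 names a rise in disc pressure immediately after injection as a possible cause of back pain. Day 1 could therefore carry a real difference unfavourable to SI-6603, and dropping it could flatter the active arm. Subjects are asked to rate pain from the herniation, which may keep procedure pain out, but the documents cannot settle that. A reader might infer that the rule understates the early effect; the documents do not support that as a firm statement.

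**The dilution factors rest on an assumption.** No passage says that the effect is zero on Day 1 and constant from Day 2. The factors also take the average without Day 1 as the truth, whereas the plan defines the time point by the seven days before the visit. This stands too, so the factors are illustrations only.

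**A wholly pre-injection score might also enter.** If randomisation was on Day -1 and the Week 1 visit on Day 7, the seven prior days reach Day -1. A reader might infer that this score is averaged in, giving 2/7 = 28.6% pre-injection or injection-day content. The text does not go that far. Protocol 9.2.2 lets Visit 2 begin on Day -1, but Protocol 9.2.3 and both schedules put Visit 2 treatment on Day 1. If the previous visit means the injection day, the existing rule removes Day -1; if it means the randomisation day, it does not. The SAP calls injection after the randomisation date rare. What remains is an ambiguity.

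**No trial conclusion depends on Week 1.** Under SAP 7.3.4, p-values outside the primary and key secondary tests may be reported but count as non-significant. This sets the size of the point, but the Week 1 comparison is still reported.

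**Conclusion.** The point holds as a small definitional gap. For Week 1 visits on Day 7 or Day 8, the leg and back pain averages contain an injection-day score whose recall includes pre-injection hours. Its weight is 1/6 or 1/7 with a complete diary and at most 1/3. This follows from the plan's own day numbering and needs no assumption. Whether a Day -1 score can also enter is unsettled for the few subjects randomised the day before injection and seen on Day 7.

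The effect on the Week 1 difference is less certain. Under the stated assumption it is a dilution of about 14–17% with a complete diary; with procedure-related pain differing by arm, it could go either way.

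A reader might infer that the primary result is compromised. It is not: the Week 13 and Week 52 windows contain no injection-day score. Week 1 reaches those estimates only indirectly, as another repeated measure in the model. That influence is judged negligible by reasoning, not by calculation.

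**What to change.** Add a third exclusion to SAP 7.3.2.1 and Protocol 11.8.1, for leg and back pain: diary scores dated on or before the injection date are not eligible for any post-baseline average. Keep the three-score minimum. The same sentence settles the Day -1 ambiguity and covers the fallback intervals.

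The cost is one sentence and one line of code, to be settled before unblinding. Week 1 averages would rest on up to 5, 6 or 7 scores for visits on Day 7, 8 or 9. A subject with Day 1 and only two other scores would drop below the minimum in that interval.

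Injection-day pain would no longer be in the Week 1 average. Leg and back pain would still be captured as adverse events of special interest (Protocol 10.1.5), tabulated with a category for onset within one day of injection (SAP 8.2.3). The change does not clear procedure-related pain from Week 1: Protocol 6.6.3 recognises a three-day post-injection period, most of which remains. Its purpose is only to keep pre-treatment recall out of a post-treatment average.

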5.2 Protocol Deviations

Protocol deviations will be categorized as major or minor prior to database lock and unblinding according to Protocol Deviation Plan. Additionally, deviations are categorized whether they are related to the COVID-19 pandemic. All recorded protocol deviations and their categorization will be presented in a listing.

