7.3.2.2 Sensitivity analyses

As a sensitivity analysis, missing data for participants in the mITT population will be imputed via MI. Twenty repeats of the imputation will be performed using Markov Chain Monte Carlo (MCMC) assuming non-monotone missing. Where the subject was discontinued due to lack of efficacy, due to an AE (with the exception of COVID-19), the subject has met the criteria for treatment failure as described in Section 7.3.3.4, or the subject's values are censored due to a prohibited therapy as described in Section 7.3.2.1, missing values will be imputed drawing from the baseline values, conditioned on the non-missing post-baseline values, of all participants in the mITT population under the assumption that they are missing not at random (MNAR); duration of leg pain will be included as a covariate.

If the study medication was discontinued for any other reason, values will be imputed within treatment group using MI under the assumption that they are missing at random (MAR) with covariates for duration of leg pain, and the weekly average worst leg pain score recorded at each time point (including baseline). The MAR approach will also be applied for sporadic missing values (prior to discontinuation). Values missing due to COVID-19, whether the result of early termination or sporadic missing values, are assumed MAR and unrelated to the endpoint of the weekly average VAS worst leg pain.

Data will be imputed for the full set of visits as described above and the same output will be used as a sensitivity for both the primary at Week 13 and the secondary endpoint at Week 52.

The MMRM analysis as described for the primary will be repeated for each of the 20 sets of data and combined using SAS PROC MIANALYZE. See Appendix [13.2](#) for the list of random seeds.

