7.3.2.3 Per Protocol Analyses

The primary analysis and the key secondary analyses will be repeated on the PP population.

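### Should Week 13 leg pain be scored from in-window days when the visit falls outside Day 85–106, as is done at Week 52?

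*SAP*

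**What the plan says.** The default in SAP 7.3.2.1 is tied to attendance: "Anchored by the visit date, the average of the consecutive days prior to each visit will be calculated". If fewer than 3 scores precede the visit, the program searches 7-day intervals anchored inside the protocol window and takes the valid one closest to the target day. The same search covers absentees: "If an in-person visit is missing altogether, the above process will be used with the corresponding visit target day".

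A visit date outside the window is not itself a trigger for that search, with one exception: "for the Week 52 visit only, if the actual visit day falls outside of the protocol-defined window, intervals in that window will be targeted" first. The Week 52 steps then begin "Each day from day 351 to day 379 will be identified as a possible anchor", and the late or early visit is used only as a last resort. No reason is given for confining this to Week 52.

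The protocol's counterpart (11.8.1) is also visit-anchored but has no search. With fewer than 3 days available, "the worst leg pain score will be handled as missing at the time point".

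On robustness, SAP 7.3.2.2 describes one analysis, in which "missing data for participants in the mITT population will be imputed via MI". SAP 7.3.2.3 adds: "The primary analysis and the key secondary analyses will be repeated on the PP population". Which subjects leave that population depends on SAP 5.2: "Protocol deviations will be categorized as major or minor prior to database lock and unblinding according to Protocol Deviation Plan".

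**The concern.** The primary estimand is the change at Week 13, yet the days that represent Week 13 depend on whether and when the subject attended. The SAP's own Week 52 rule makes this look like an oversight. Subjects with too few scores before the visit are already caught by the general search, so the Week 52 rule changes a score only when a usable out-of-window average exists. It therefore expresses a preference for in-window timing in itself, and that preference is withheld from the primary time point.

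Nothing planned seems to test the choice. Multiple imputation leaves an observed out-of-window average untouched. The per-protocol repeat uses the same derivation, and would help only if visit timing counts as a major deviation under a plan the documents do not reproduce.

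There is also a conceivable mechanism. Protocol 6.7.1 bars block procedures for LDH symptoms only before Week 13, and SAP 7.3.2.1 does not remove days after a block. A late visit could therefore be scored after a permitted block. If late attendance differed by arm, or the treatment difference changed after the window, the primary estimate would move.

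**Working it through.** **Design figures.** SAP 2.6 gives a difference of 12 mm, SD 30 mm, two-sided 5%, power 90%, dropout 15% and 160 per arm.

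- Normal approximation: n = 2(1.960 + 1.282)² × 30² / 12² = 131.3, so 132 per arm; 132 / 0.85 gives 156.
- Exact t-test: 133 per arm; 133 / 0.85 gives 157. The plan's 160 is reproduced to within 3%.
- Completers: 160 × 0.85 = 136 per arm. SE = 30 × √(2/136) = 3.638 mm. Power at 12 mm is 0.910 (normal) or 0.908 (t).

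**The rule with a complete diary.** The Week 13 window (protocol 9.2.7) is 92 − 7 = Day 85 to 92 + 14 = Day 106. A visit on Day V uses Days V − 7 to V − 1.

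| Week 13 visit | Days scored |
|---|---|
| Day 80 | 73–79 |
| Day 92 | 85–91 |
| Day 106 | 99–105 |
| Day 120 | 113–119 |
| Day 130 | 123–129 |
| Missed | 85–91 |

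In-window anchors draw on Days 78–105. Visits on Days 79–84 or 107–112 therefore still share 1 to 6 scored days with that range. Only visits by Day 78 or from Day 113 lie wholly outside it. Among compliant visits the anchor already varies by 106 − 85 = 21 days.

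**Size.** The documents give neither the share of out-of-window visits nor the drift in pain, so both are assumed. Let a share f of each arm be out of window, and let the treatment difference on those days differ by d mm from that on the same subjects' in-window days. The estimate then moves by about f × d.

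| f | d = 1 mm | d = 3 mm | d = 5 mm |
|---|---|---|---|
| 5% | 0.05 | 0.15 | 0.25 |
| 10% | 0.10 | 0.30 | 0.50 |
| 15% | 0.15 | 0.45 | 0.75 |

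In units of the SE this is 0.05 / 3.638 = 0.01 to 0.75 / 3.638 = 0.21. At the far end, 12 − 0.75 = 11.25 mm and power is 0.871. If lateness also differs between arms by 5 percentage points and late scores differ by 5 mm, add 0.05 × 5 = 0.25 mm. That gives 11.00 mm and power of about 0.856.

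A harsher assumption puts 20% of one arm only out of window, with a 10 mm shift against SI-6603. This moves the estimate by 0.20 × 10 = 2.0 mm and gives power 0.782 (t). An equal share and equal shift in both arms cancel.

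**Block procedures.** If Week 13 in protocol 6.7.1 means Day 92, a Day 130 visit leaves Days 92–129 (38 days) in which a permitted block could precede or fall in the scored week. A compliant Day 106 visit leaves Days 92–105 (14 days). If it means the visit itself, the count is zero in both cases. Either way, the SAP 7.3.1 estimand censors only after the listed surgical and intradiscal procedures and takes other data as observed. Days after a permitted block therefore belong to the declared estimand.

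**What a re-anchored analysis would show.** Using the Week 52 steps at Week 13, the Day 130 subject moves to Days 85–91. The Day 106 subject stays on Days 99–105 and the absentee on Days 85–91, so dependence on attendance remains within the window. A Day 80 subject moves from Days 73–79 to Days 85–91, which is 5 to 11 days after the visit.

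**The case for a change.** The best case for acting is that an analysis based on the existing Week 52 program costs little, leaves the primary p-value alone, and is credible only if written down before unblinding. The asymmetry with Week 52 is real and unexplained. The description of the rule stands in full.

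The claim that acting would improve the plan does not stand. Protocol 11.8.2 states that follow-up data are analysed by actual visit date and that out-of-window assessments stay with the visit recorded in the eCRF. SAP 7.1.2 keeps the actual-visit principle. The rule for absentees is a fallback: with no visit date, the target day is the natural anchor. Protocol 6.6.4 times the suspension of hydrocodone/acetaminophen to the visit, so re-anchored days may include its use. For early attenders they would also follow the visit, and they would no longer be concurrent with ODI, neurologic status and MRI. A gap between the two results could not be put down to timing alone.

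It is also too strong to say that nothing looks at timing. Protocol 11.6.3 and 11.8.1 plan weekly scores by treatment group irrespective of visit date. That display is descriptive and SAP 7.3.3.3 does not repeat it, so it is context rather than a formal check. Protocol 9.2.7 also requires contact at least 14 days before the Week 13 visit, which should limit very late attendance.

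SAP section 11 does not list the in-window search or the Week 52 rule as departures from protocol 11.8.1. That is a clerical omission: SAP 7.3.2.1 spells both out, and listing them would alter no result.

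**Conclusion.** No change to the plan is needed. Scoring Week 13 from the days before the actual visit is prespecified, treats the arms alike and follows the protocol's stated convention. Preferring in-window days would be a trade-off, gaining closeness to Day 92 and losing alignment with the visit's other assessments and with the rescue-medication suspension. It would not correct an error.

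No bias is shown, and direction and size are unknown. Under the main assumed range (5–15% out of window in each arm, 1–5 mm) the shift is at most 0.75 mm, about a fifth of the planned standard error. It reaches 1.00 mm with the assumed imbalance between arms. Only a one-sided pattern such as 20% with a 10 mm shift makes it material (2.0 mm), and nothing in the documents points to that. A count of out-of-window Week 13 visits by arm, or one re-anchored run, would do no harm. It would speak only to those visits and would not change the primary conclusion.
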